10.1. Definitions

The following definitions will apply to the reporting of adverse events:

1. Serious Adverse Event: Any adverse experience occurring at any dose that is fatal or life threatening; requires in-patient hospitalization or prolongation of an existing hospitalization; is a persistent significant disability/incapacity; is a congenital anomaly or birth defect; or is an important medical event that may not result in death, be life-threatening, or require hospitalization but, based upon appropriate medical judgment, may jeopardize the subject and may require medical or surgical intervention to prevent one of the outcomes listed above.
2. Unexpected Adverse Event: Any adverse experience that is not identified in nature, severity, or frequency in the Investigator's Brochure for NTZ.
3. Severity of adverse events will be assessed by the Investigator using the Toxicity Grading Scale Tables provided in [Appendix II](#) (derived and adapted from “Guidance for Industry: Toxicity Grading Scale for Healthy Adult and Adolescent Volunteers Enrolled in Preventive Vaccine Clinical Trials”, US Dept. of HHS, FDA, CDER, September 2007 and the National Institutes of Health, National Cancer Institute Common Terminology Criteria for Adverse Events (CTCAE) version 5.0).

4. Causality (relationship to treatment) will be assessed as follows:

- *Definitely Related*: The adverse event is clearly related to the investigational agent(s) or research intervention: the adverse event has a temporal relationship to the administration of the investigational agent(s) or research intervention, follows a known pattern of response, and no alternative cause is present.
- *Probably Related*: The adverse event is likely related to the investigational agent(s) or intervention: the adverse event has a temporal relationship to the administration of the investigational agent(s) or research intervention, follows a known or suspected pattern of response, but an alternative cause may be present.
- *Possibly Related*: There is a reasonable possibility that the event may have been caused by or is linked in a significant way to the research; the adverse event has a temporal relationship to the administration of the investigational agent(s) or research intervention, follows a suspected pattern of response, but an alternative cause is present.
- *Unrelated (or Not Related)*: The adverse event is clearly NOT related to the investigational agent(s) or intervention: the adverse event has no temporal relationship to the administration of the investigational agent(s) or research intervention, follows no known or suspected pattern of response, and an alternative cause is present.

Under double-blind treatment conditions, it should be assumed that all subjects are taking the test drug.

10.2. Clinical Adverse Events

At the time of each return visit, the subject will be questioned regarding the occurrence and nature of any adverse events. All events must be recorded in the subjects' medical records and in the EDC system. Any subject affected will be examined by the Investigator as deemed necessary to ascertain the course of the event and any residual effects.

All moderate and severe adverse events will be reviewed by the Principal Investigator who will determine using his/her best clinical judgment whether they warrant the subject to be discontinued from the study. The Sponsor will be notified immediately if a subject is discontinued from the study. For all adverse events that require the subject to be discontinued from the study, relevant clinical assessments and laboratory tests will be repeated as clinically indicated until final resolution or stabilization of the event(s).

All subjects will be instructed to contact the Investigator, Investigator's assistants, or clinical personnel should the subject have any serious adverse experiences. Serious adverse events, including death regardless of the cause, must be reported to the Sponsor immediately (within 24 hours of the initial report).

A serious event requiring immediate notification by telephone is an event that:

- results in death
- is life threatening

- requires inpatient hospitalization or prolongation of an existing hospitalization
- is a persistent or significant disability/incapacity
- is a congenital anomaly/birth defect
- an important medical event that may not result in death, be life-threatening, or require hospitalization but, based upon appropriate medical judgment, may jeopardize the subject and may require medical or surgical intervention to prevent one of the outcomes listed above.

An overdose is defined as any intentional or unintentional consumption of the drug by any route that exceeds the highest dose stated in the Investigator's Brochure or in an investigational protocol, whichever dose is larger. Overdoses without an associated adverse event should be recorded, but not reported as an adverse event.

10.3. Reporting Requirement

The Principal Investigator is required to notify The Romark Institute for Medical Research (Sponsor) immediately of any unexpected, fatal, or life-threatening experience and all unusual, alarming, or serious reactions to medication regardless of any opinions as to the cause/effect relationship. All serious adverse events will also be reported to the IRB. Adverse events should be reported to:

The Romark Institute for Medical Research
Medical Affairs
[REDACTED]
[REDACTED]
[REDACTED]
[REDACTED]

10.4. Medication Modification/Withdrawal Due to an Adverse Event

If a severe adverse reaction develops during therapy, the study medication should be discontinued, and the subject should be withdrawn from the study.

10.5. Medication Errors

A medication error is defined as any preventable event related to dosing instructions, product labeling, or packaging that causes or leads to inappropriate medication use or subject harm while the medication is in the control of the investigative site or subject. Medication errors which result in adverse events should be recorded and reported as adverse events. All other medication errors should be reported to the study Sponsor through the Medical Affairs department within 7 days of identification by the site.

11. DISCONTINUATION

11.1. Study Discontinuation

The study may be discontinued under the following circumstances:

1. The Sponsor reserves the right to discontinue the study at any time.
2. Adverse event listings will be produced for safety monitoring at least once every two weeks during recruitment. The data will be tested to determine if there are greater than 20% of the subjects who have had \geq Grade 3 adverse events considered by the Investigator to be possibly, probably or definitely related to the study drug (defined by the Toxicity Grading Scale Tables provided in [Appendix II](#)).

If greater than 20% of the subjects have at least one Grade 3 or Grade 4 adverse event considered to be possibly, probably or definitely related to the study drug by the study Medical Monitor, then the study must be stopped and the Institutional Review Boards, and FDA's Division of Anti-Infectives will be notified. All safety and activity data will be submitted to the FDA in a timely manner.

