3. STUDY DESIGN

The study will be a multicenter, randomized, double-blind, placebo-controlled trial to evaluate the efficacy and safety of NTZ for post-exposure prophylaxis of COVID-19 and other VRIs in elderly LTCF residents.

Subjects will be randomized within strata 1:1 to one of the following groups:

- Group 1 (NTZ): Two NTZ 300 mg tablets b.i.d. for 6 weeks
- Group 2 (Placebo): Two placebo tablets b.i.d. for 6 weeks

This study is expected to run from April 2020 through December 2020.

Rationale for important issues in the study design is described below:

- *Rationale for study design.* *In vitro* data suggest NTZ may be effective against the most common viruses associated with VRIs including SARS-CoV-2. Except for influenza, there are no drugs or vaccines commercially available to prevent VRIs, especially pandemic and outbreak strains of non-influenza viruses like SARS-CoV-2. In the case of influenza these drugs are limited to only the neuraminidase inhibitors for chemoprophylaxis and the vaccine has been demonstrated to be less effective in elderly patients. This study is designed to determine if a drug with broad-spectrum antiviral activity like NTZ can prevent VRIs in at risk elderly subjects residing in LTCFs.
- *Choice of NTZ dose and duration of treatment.* The dose of NTZ was selected based upon safety, tolerability and pharmacokinetics data from prior clinical experience with nitazoxanide. Extended release tablets at a dose of 600 mg administered twice daily with food will be used to achieve and maintain steady state plasma concentrations of tizoxanide above the concentrations required to inhibit respiratory viruses in cell cultures. The tablets will be administered with a B complex vitamin (Super B-Complex™, Igennus Healthcare Nutrition, Cambridge, UK) to mask potential chromaturia that may be observed due to the yellow color of nitazoxanide metabolites. A treatment duration of 6 weeks is expected to be sufficient to capture transmission of COVID-19 yet short enough to avoid unnecessary exposure to the medication. Studies of oseltamivir for prophylaxis of influenza in the LTCF population have employed a 6-week treatment duration. That treatment duration is supported by safety data from prior studies of NTZ and past experience noting prolonged activity of non-influenza viruses that extended for several months ([Monto et al. 1987](#), [Peters et al. 2001](#), [Falsey et al. 2008](#), NTZ 300 mg Tablets Investigators Brochure).

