5.6. Week 8 Evaluation (+7 days)

A study physician, nurse or other study personnel will visit each subject at Week 8 and the following procedures will be performed:

1. Physical examination as warranted by the Investigator for any change from baseline.
2. Collection of blood sample for anti-SARs-CoV-2 antibodies.
3. Review and record concomitant medications.
4. Review and record adverse events/side effects and complications. Note that all adverse events and complications must be followed until their resolution or stabilization even beyond the 8-week study period.
5. Document any infections diagnosed during the follow-up period.

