6. RANDOMIZATION

Subjects will be randomized 1:1 by stratum to receive either NTZ or placebo. An independent third party will prepare a master randomization list and maintain the masking of the study. Subjects who qualify for the study will be assigned to treatment using centralized randomization procedures. The treatment numbers will appear on the bottles containing the masked study medication. The randomization list will be masked to study participants including Sponsor, Investigators, study monitors, statisticians, subjects and laboratory personnel. Unmasking procedures will be detailed in the Medical Monitoring Plan and Investigators will be provided instructions for unmasking.

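### The two-weekly listings that feed Protocol 11.1's only numerical safety stop are required only during recruitment, although dosing and adverse event review continue for up to 8 weeks afterwards

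*Protocol*

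**What the plan says.** Protocol 11.1 (Study Discontinuation) sets out the monitoring step: "Adverse event listings will be produced for safety monitoring at least once every two weeks during recruitment". The data are then tested against a 20% limit on Grade 3 or higher events judged possibly, probably or definitely related. The consequence follows: "If greater than 20% of the subjects have at least one Grade 3 or Grade 4 adverse event" judged related, "then the study must be stopped and the Institutional Review Boards" and the FDA division are notified. The stop sentence carries no time limit. The listing sentence does.

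Protocol 3 gives 6 weeks of dosing and the calendar: "This study is expected to run from April 2020 through December 2020". Protocol 5.6 still has adverse events on the Week 8 visit list: "Review and record adverse events/side effects and complications".

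Neither sentence of the rule names a treatment arm. Protocol 6 states: "The randomization list will be masked to study participants including Sponsor, Investigators, study monitors, statisticians, subjects and laboratory personnel". Protocol 10.1 tells those judging causality: "Under double-blind treatment conditions, it should be assumed that all subjects are taking the test drug".

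Protocol 14 leaves IDMC procedures to the Medical Monitoring (Safety) Plan and the IDMC charter, neither of which was available for this review. SAP 2.4 schedules IDMC safety reviews when 20% of planned subjects have completed 3 weeks and when 50% have completed 6 weeks. It also provides a look at 25 COVID-19 cases that includes a safety determination.

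**The concern.** A stopping rule works only while someone is required to check it. Followed as written, the plan ends the required two-weekly check when the last subject is recruited, and that subject then has 6 weeks of dosing ahead.

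This is also when the figure becomes most informative. While recruitment runs, newly entered subjects with little exposure hold the percentage down. Once it closes, and if the denominator is all subjects randomized or dosed so far (11.1 does not define it), the denominator is fixed while events still accrue. The cumulative percentage can then only stay level or rise.

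Exposure of this length is also new for this population. Protocol 1.2.3 reports 75 subjects aged 65 or over in Phase 3 trials of these tablets, all dosed for 5 days.

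**Working it through.** The 20% limit and the listing interval are stated without derivation, so there is no figure of the plan's to reproduce.

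**Inputs.** 800 subjects, 400 per arm (Protocol 8.1); 6 weeks of dosing (Protocol 3); last review at Week 8 (Protocol 5.6); study period April to December 2020 (Protocol 3). Assumed: uniform accrual, no dropout, and recruitment ending at the last randomization.

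**Length of recruitment.** 1 April to 31 December 2020 is 274 days, or 39.1 weeks. If the last subject is to finish 8 weeks of follow-up inside that period, recruitment lasts at most 39.1 − 8 ≈ 31 weeks. A range of 22 to 35 weeks is used. The upper end allows for follow-up running past December.

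**Subjects still exposed when recruitment closes.** With *W* weeks of recruitment, those entered in the last 6 weeks are still on treatment, 800 × 6 / *W*. Those entered in the last 8 weeks have not reached Week 8, 800 × 8 / *W*.

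| *W* (weeks) | Still on treatment | Not yet at Week 8 |
|---|---|---|
| 22 | 218 | 291 |
| 31 | 155 | 206 |
| 35 | 137 | 183 |

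**Share of dosing time.** Under uniform accrual, those still on treatment have 3 weeks left on average. At 31 weeks that is 155 × 3 = 465 of 800 × 6 = 4,800 subject-weeks, about 10%. The general form is 3 / *W*, or 14% at 22 weeks and 9% at 35.

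**Do the scheduled IDMC reviews cover the gap?** At 31 weeks, subject 160 (20% of 800) enters at week 6.2 and completes 3 weeks at week 9.2. Subject 400 (50%) enters at week 15.5 and completes 6 weeks at week 21.5. At 22 weeks the second review falls due at 11 + 6 = 17; at 35 weeks, at 17.5 + 6 = 23.5. In each case both reviews come due before recruitment closes. The 25-case look depends on COVID-19 counts, and SAP 2.4 expects only 24 events in the whole study under the design assumptions.

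**Secondary note: what the 20% refers to.** If the rate is pooled with equal arms, it equals (NTZ rate + placebo rate) / 2. It exceeds 20% exactly when the NTZ rate exceeds 40% minus the placebo rate. The documents give no related Grade 3–4 rate, so the placebo rates here are assumed: NTZ must exceed 38% at placebo 2%, 35% at 5% and 30% at 10%. With all 800 subjects evaluable, at least 161 must be affected.

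**The case against.** **On the listings.** This can be called a wording point. Two-weekly is a minimum, the stop sentence has no end date, and adverse events are recorded and followed after recruitment. Serious events reach the sponsor within 24 hours (Protocol 10.2), and the sponsor may stop the study at any time. Individual protection also continues: "If a severe adverse reaction develops during therapy, the study medication should be discontinued, and the subject should be withdrawn from the study". All of this stands. What lapses is the scheduled check, not the criterion or the data collection. The counts depend on uniform accrual, which is doubtful because entry requires a recent COVID-19 case in the facility and so may come in bursts. A late burst would raise the counts; a slow finish would lower them. None of this gives a reason to end the check while subjects are still being dosed.

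**On pooling.** A reader might infer that the rule cannot detect toxicity in the NTZ arm and that the plan needs a numerical NTZ-arm threshold. One calculation points that way. At assumed rates of 30% on NTZ and 5% on placebo, the pooled rule trips with probability 47% over 15 looks (39% to 52% for 18 to 11 looks, in whichever order). A check that requires the NTZ rate to be above 20% and above placebo, from 80 NTZ subjects on, trips almost always. The documents do not support going that far, for four reasons:

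- Pooling is inferred. The rule names no arm, and the masked list in Protocol 6 mentions neither the medical monitor nor the IDMC.
- Every event rate is assumed. Prior experience is reassuring: Protocol 1.2.4 reports that under 1% stopped therapy for adverse events. At NTZ rates of 10% or less nothing material is lost.
- The comparison sets a mandatory study stop against a trigger that would only prompt an IDMC review, and IDMC reviews already exist.
- By-arm review may already be in the charter or safety plan. An added threshold has its own cost: with no drug effect, the check just described trips in 13% of trials at a 15% rate in both arms and in 44% at 18%. Its 80-subject floor and lack of a margin over placebo are arbitrary, and it needs frequent unblinded output.

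**Conclusion.** The point holds for the listings. As written, Protocol 11.1 ends the required check on its only numerical safety stop while about 155 of 800 subjects (137 to 218) are still on treatment and about 206 (183 to 291) have not reached Week 8. About a tenth of planned dosing time falls after that moment. These figures rest on uniform accrual over an assumed 22 to 35 weeks and no dropout. That some subjects are still being dosed when recruitment closes follows from the 6-week regimen alone.

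The pooled reading is a secondary note and not a demonstrated defect. The 40%-minus-placebo arithmetic is exact for equal arms, and a pooled rule is a reasonable masked backstop. Whether by-arm review is missing cannot be judged without the charter and safety plan. Overall this is a change to consider: small, specific and close to free.

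**What to change.** In Protocol 11.1, replace 'during recruitment' with 'until the last subject completes the Week 8 visit'. The cost is about 8 more weeks of two-weekly listings, roughly four, or one more if the last visit uses its 7-day allowance. They draw on adverse event data that are already collected. There is no effect on masking, sample size or the efficacy analysis.

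Keep the 20% rule and its mandatory stop as they are. Add one sentence to 11.1 saying that the rate is taken over both arms together, if that is the intent, and citing the section of the IDMC charter that provides for by-arm safety review. Leave any numerical arm-level trigger to the IDMC. If the charter has no by-arm review, that is for the sponsor and the IDMC to settle there. The cost is a cross-reference.

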11.2. Subject Discontinuation

Treatment will be discontinued for individual subjects for the following reasons:

1. An allergic reaction occurs or is suspected.
2. Medical conditions that may require study discontinuation in the Investigator's judgment.
3. Subject desire to discontinue participation.

In the case of an allergic reaction or other medical condition requiring subject discontinuation, appropriate treatment will be instituted by the Investigator.

12. ELECTRONIC DATA COLLECTION (EDC) SYSTEM

An EDC system will be used for this study. Prior to study initiation, site staff and authorized Romark personnel will be trained to use this system.

All source forms are to be filled out completely by the examining site staff and reviewed and signed off on by the Investigator(s).

13. RETENTION OF RECORDS

Essential Documents are documents that individually and collectively permit evaluation of the conduct of a trial and quality of the data produced. They demonstrate the compliance of the Investigator, Sponsor, and monitor with the GCP standards and with all applicable regulatory requirements.

In compliance with the ICH/GCP guidelines, the Investigator/institution will maintain all CRFs and all EDC source forms and source documents that support the data collected from each subject, as well as all study documents as specified in ICH/GCP Section 8, Essential Documents for the Conduct of a Clinical Trial, and all study documents as specified by the applicable regulatory requirement(s). A list of these documents is found in [Appendix III: List of Essential Document for the Investigative Site](#). The Investigator/institution will take measures to prevent accidental or premature destruction of these documents.

Essential documents listed in [Appendix III](#) must be retained for the duration required by applicable regulatory authorities or until the Sponsor informs the Investigator/institution these documents are no longer needed.

If it becomes necessary for the Sponsor or the appropriate regulatory authority to review any documentation relating to this study, the Investigator must permit access to such reports.

The Sponsor is responsible for organizing and maintaining the Trial Master File which is a clear documentation of the course of the study.

14. MONITORING THE STUDY

Monitoring will be conducted by the Sponsor and/or a contract research organization according to standard operating procedures. Site visits will be conducted by the Sponsor or their representatives at regular intervals to conduct inspections.

A full description of the monitoring procedures for this study will be detailed in the Clinical Monitoring Plan.

The Investigator will grant representatives of the Sponsor's clinical operations team and quality team, as well as regulatory agencies and ethical committees access to inspect facilities and records (including subject charts) relevant to this study and agrees to assist the monitors in their activities, if requested.

An Independent Data Monitoring Committee (IDMC) will be organized for this study. A full description of the IDMC procedures for this study will be detailed in the Medical Monitoring (Safety) Plan and IDMC Charter. The IDMC will closely monitor the incidence of diarrhea as it could potentially be a vehicle for the spread of SARS-CoV-2. Enrollment will be paused while the IDMC conducts its first interim analysis of safety and futility. The IDMC may also conduct analyses of safety, futility and effectiveness if the number of COVID-19 illnesses is higher than anticipated.

15. INFORMED CONSENT

Each subject must give written consent according to local requirements after the nature of the study has been fully explained. The informed consent form (ICF) must be signed before performance of any study-related activity. The informed consent form will be approved by both the Sponsor and by the reviewing IRB. They will be in accordance with principles that originated in the [Declaration of Helsinki](#), current ICH and GCP guidelines, applicable regulatory requirements, and Sponsor policy.

Before enrollment in the study, the Investigator or an authorized member of the investigational staff must explain to potential subjects the aims, methods, reasonably anticipated benefits, and potential hazards of the study, and any discomfort participation in the study may entail. Subjects will be informed that their participation is voluntary and that they may withdraw consent to participate at any time. They will be informed that choosing not to participate will not affect the care he/she will receive. Finally, they will be told that the Investigator will maintain a subject identification register for the purposes of long-term follow-up if needed and that their records may be accessed by health authorities and

authorized Sponsor staff without violating the confidentiality of the subject, to the extent permitted by the applicable law(s) or regulations. By signing the ICF the subject is authorizing such access, and agrees to allow his or her study physician to re-contact the subject for the purpose of obtaining consent for additional safety evaluations, if needed.

The subject will be given sufficient time to read the ICF and the opportunity to ask questions. After this explanation and before entry into the study, consent should be appropriately recorded by means of the subject's personally dated signature. After having obtained the consent, a copy of the ICF must be given to the subject.

If the subject is unable to read or write, an impartial witness should be present for the entire informed consent process (which includes reading and explaining all written information) and should personally date and sign the ICF after the oral consent of the subject is obtained, if permitted by local law.

Signed ICFs must remain in the subject's file(s) and be available for verification by representatives of Romark, the IRB, and FDA/relevant regulatory agencies at any time.

